Potential patients will be checked for fulfillment of the previously mentioned inclusion criteria. Every participant will be asked to sign an informed consent about the study. Full set of records (study models, lateral cephalometric radiographs, photos) will be taken for every patient as part of the routine procedure for treatment of patients in the clinic of the Orthodontic Department at The Future University of Egypt.

➤ Clinical Procedure:

After taking pre-treatment records:

- Bonding of all teeth except for first premolars and banding/bonding the first and second molars will be done using Roth prescription brackets (0.022 slot).

- Leveling and alignment for the bonded and banded teeth will be initiated following the wire sequence: 0.014 NiTi, 0.016×0.022 NiTi and 0.017×0.025 StSt.
- Then miniscrews will be placed in upper and lower arches between 2nd premolar and 1st molar.
- The patient will be referred for extraction of 1st premolars then canine retraction on a 0.017×0.025 StSt arch wire.
- After canine retraction, the patient will be referred for the pre-intervention records.

➤ **Acquisition of pre-intervention records:**

- The patient will be referred for CBCT which is considered to be the T0 record.

➤ **Start of Retraction:**

Frictionless group:

- A ligature wire will be extended between the canines and miniscrews for proper anchorage control.
- Closing retraction T-loops will be fabricated using 0.017 x 0.025 TMA wire. The loop will be positioned halfway the remaining extraction space after canine retraction. [17], [22].
- A gable angle of 45° will be added.
- Distal activation of 4 mm will be done which produced around 160 g of force per side with cinching back the wire distal to molars bilaterally.[23].
- Reactivation will be only done when the two arms of the t-loop approximate 2-3 mm.

Friction group:

- Miniscrews will be checked for stability. In case of any dislodgment or instability, they will be removed and replaced.
- A crimpable hook of 8mm length will be added to the archwire (0.017"x0.025" Stainless steel) distal to the lateral incisors passing through the center of resistance of the anterior segment.
- A ligature tie will be tightly wound from an undercut in the miniscrew head to canine bracket to stabilize the posterior segment.
- Retraction will start on a 0.017"x0.025" Stainless steel archwire using elastomeric power chain (force applied will be 160 g per side) extending between the crimpable hook and the miniscrew head.

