- The force will be measured by a force gauge and reactivated every 4 weeks maintaining constant force of retraction all over the retraction phase.

➤ **Follow up visits**

Patients will be asked to attend for follow up sessions every 4 weeks for:

- Evaluation mini-screws stability.
- Replacement of the power chain to maintain a force of 160 gm per side.
- Reactivation of the T-loop by further distal activation and cinch back if needed.

➤ **Criteria for discontinuing or modifying the allocated intervention:**

In cases of prolonged swelling or pain related to the mini-screw the patient will be given strict oral hygiene measures and the beginning of retraction will be postponed for three weeks.

In cases of loose or broken mini-screws, the screw will be removed and replaced.

➤ **Retraction records**

Following retraction of the anterior segment, patients will be referred to the same radiology center to acquire the final CBCT to assess the movement and inclination of anterior teeth.

➤ **Materials**

- American Orthodontics Brackets, Roth prescription, 0.022 slot size.
- American Orthodontics Elastomeric power chains.
- American Orthodontics Elastomeric O-ties.
- American Orthodontics Ligature wire.
- Mini-screw (1.6- by 8-mm, bracket head design; Dual Top Anchor System, Jeil Medical Corporation, Seoul, Korea).
- American Orthodontics Arch wires.
- American Orthodontics Molar bands/tubes.
- Crimpable hooks (Dentos Inc.)

D] Outcomes

[figure not shown]
Primary outcome: is to monitor the changes in the anterior teeth position (final anterior teeth tip, torque and vertical position) in association with each technique after retraction

Secondary outcomes: are to detect the presence of any root resorption associated with the different methods used for anterior segment. All outcomes

will be assessed as the difference between T0 at the start of anterior segment retraction after full canine retraction and T1 after complete space closure.

E] Participant timeline:

1. The principle investigator will screen the potential patients through careful clinical examination of patients at the orthodontic department, Faculty of Oral and Dental Medicine at The Future University of Egypt.
2. All recruited patients must fulfil the previously mentioned inclusion and exclusion criteria.
3. Every participant will be asked to sign an informed consent before the beginning of the study.

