4. After patient's enrolment, each participant will be asked for pre-intervention records to ensure proper diagnosis.
5. The co-supervisor will randomly allocate the patients to one of the intervention groups.
6. Active intervention will start after proper leveling and alignment of the upper and lower arches and canine retraction.
7. The principle investigator will take pre-retraction records for every participant (T0).
8. In Friction mechanics group, Power chain will be used for anterior segment retraction while in Frictionless group, T-loop will be used for retraction.
9. Each patient will come every 4 weeks for the follow up visit, for appliance activation and impressions for interim records.
10. After complete space closure, the principle investigator will take post-retraction records for each participant (Tfinal).
11. The principle investigator will continue the normal treatment and achieve proper finishing for every patient after the end of the study.

E] Sample size calculation:

In a previous study by **Dincer et al.** [1], they compared the effect of frictionless mechanics via PG spring (Poul Gjessing spring) (Group I) and friction mechanics using coil spring (Group II). The mean change in distance between central incisor edge and x-axis was of 0.68mm and SD of 0.73 in Group I, while Group II was -0.32mm and SD of 0.79.

Sample size calculation was done based on that study using PS software output. A continuous response variable from independent Group I and Group II subjects was planned. In the previous study, the response within each subject group was normally distributed with standard deviation 0.76. If the true difference in the Group II and Group I means is 1.0, we needed to study 10 Group II subjects and 10 Group I subjects to be able to reject the null hypothesis. The population means of the Group II and Group I are equal with probability (power) 0.8. The Type I error probability associated with this test of this null hypothesis is 0.05. Considering drop out a sample size of 15 per group was planned (**Figure 1**).

[figure not shown]

Figure 1: Power curve for 2-sample t-test denoting the power of the study.

Statistical Methods

All statistical calculations will be done using computer program IBM SPSS (Statistical Package for the Social Science; IBM Corp, Armonk, NY, USA) release 22 for Microsoft Windows.

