Blinding of the outcome assessors: It is a single blinded study, the outcome assessors only will be blind. The patients name will be sealed from pre and post records. Then two assessors will carry on, blindly and independently, the measurements and analysis of the study.

III) Data collection, management and analysis:

A] Data collection methods:

Primary outcome:

1. *Anterior teeth torque, extrusion/intrusion:* will be assessed by the principle investigator via CBCT taken before and after the completion of retraction. The principal investigator identified the landmarks, reference lines and planes, then interpreted the measurements in degrees and millimeters.

2. *Anterior teeth tip:* will be assessed by the principle investigator via CBCT taken before and after the completion of retraction.

Secondary outcomes:

1. *Root resorption:* will be assessed by the principle investigator via CBCT taken before and after the completion of retraction. The resorption will be identified using scoring system of Levander and Malmgren[21] that classifies it into 5 grades: 0: no root resorption; 1: mild resorption, with the root of normal length and only an irregular contour; 2: moderate resorption, with small areas of root loss and the apex having an almost straight contour; 3: severe resorption, with loss of almost one third of root length; and 4: extreme resorption, with loss of more than one third of the root length.

B] Data management:

A colleague outside the research team will enter the data and organize it in excel sheets in the computer of the orthodontic department.

Data will include all photographs, models and radiographs.

C] Statistical Analysis:

- The principle investigator will be responsible for the extraction of the required data from the CBCT taken before and after retraction. The data will be sent to a specialized statistician.

- The specialized statistician will be responsible for the statistical analysis of the study by:

1. Presenting the data as mean, standard deviation (SD) and Standard error (SE) values.

2. Using Paired t-test to compare between the friction and the frictionless group of retraction as well as to compare between the pre-and post -treatment data for each group.

3. Using Anova test to determine the rate of anterior segment retraction.

4. Statistically evaluate the patient acceptance for both techniques.

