A] Research Ethics Approval:

The Ethical committee in Future University, Egypt will review the protocol before they approve it. The research Ethics committee will evaluate the different interventions of the study to ensure its ethical validity and the potential benefits to the participants.

B] Protocol amendments:

The main investigator will be responsible to complete a formal amendment in case of any modifications or adjustments to protocol that may affect the conduct of the study, as changes in the study design or intervention procedures. The Orthodontics department, Faculty of Oral and Dental Medicine, Future University and the Ethics Committee will approve such amendment before proceeding in the study .

C] Consent:

The main investigator will be in charge for detailed explanation and elaboration of the different steps of the study interventions for each patient. Then will ask every participant to sign a written consent before they begin treatment. The consent will be written in Arabic.

D] Confidentiality:

The main investigator will store any personal information about the participants collected during the study separately from study records in locked files in areas with only access to the supervisors responsible for auditing and analysis. Also, will keep the files in the Department Of Orthodontics, Faculty of Oral and Dental Medicine, Future University and will identify all the reports, data and administrative forms by a coded ID number to maintain participant confidentiality. Participant information won't be used outside the study except with written permission of the participant.

E] Declaration of interests:

No financial interests are to be declared by the supervisors and the principle operator. This study is a part of a Masters' degree in Orthodontics, Faculty of Oral and Dental Medicine, Future University and it is self-funded by the principal investigator.

F] Access to data:

The supervisors and the principal investigator will only have access to the data of the study. All the data will be secured by a password to maintain confidentiality. No

other parties are allowed to assess the results until the study is terminated and the conclusions are revealed.

G] Ancillary and post-trial care:

Any complication associated with the intervention will be managed by the principal operator. Then the two group of patients will continue their regular orthodontic treatment according to the treatment plan described for each case.

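### The stated means of blinding the outcome assessors hide who the patient is, not which arm she is in, and the protocol contradicts itself on who measures the CBCTs

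*Combined protocol and SAP*

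**What the plan says.** All places are in the combined protocol and SAP.

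- **Blinding (II, D).** Operators are not blinded. For assessors: "It is a single blinded study, the outcome assessors only will be blind". The means given is: "The patients name will be sealed from pre and post records". It continues: "Then two assessors will carry on, blindly and independently, the measurements and analysis of the study".
- **Confidentiality (V, D).** The main investigator "will identify all the reports, data and administrative forms by a coded ID number".
- **Start of Retraction, frictionless group.** "Closing retraction T-loops will be fabricated using 0.017 x 0.025 TMA wire".
- **Start of Retraction, friction group.** "A crimpable hook of 8mm length will be added to the archwire", placed distal to the lateral incisors on a stainless steel wire.
- **Retraction records.** "Following retraction of the anterior segment, patients will be referred to the same radiology center to acquire the final CBCT". Nothing is said about which appliance parts are in the mouth at that scan, or about processing the images before they are read.
- **Participant timeline.** The principal investigator takes the records before and after retraction. The last item reads: "The principle investigator will continue the normal treatment and achieve proper finishing for every patient after the end of the study".
- **Data collection methods (III, A).** Torque, extrusion/intrusion, tip and root resorption are each assigned to the principal investigator, working from the CBCTs. Statistical Analysis (III, C) has the same person extract the CBCT data.

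**The concern.** Every primary outcome depends on a person placing landmarks, lines and planes on a CBCT. The secondary outcome is a five-grade visual score. Readings of this kind can drift toward what the reader expects, and the introduction sets out an expectation that loops control the incisors better than sliding mechanics. Blinding the reader is the trial's only protection against that drift.

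The protection can fail by two separate routes. First, the image may show the arm even when the name and ID do not. Second, the person measuring may know the arm already. The first would remain with two outside readers; the second would remain with perfectly masked images. More patients do not help: the shift stays the same size while the standard error shrinks, so its effect on false positives grows.

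**Working it through.** **1. What each masking step hides.** A sealed name and a coded ID both conceal which patient is being read. Neither removes anything from the image that differs between the arms.

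**2. What could show on the scans.** The pre-retraction scan (T0) comes after canine retraction and before the loop or hook is described as fitted, so it should not separate the arms. The final scan (T1, called Tfinal in the timeline) follows anterior retraction, and finishing follows later, so fixed-appliance treatment is still under way. The metal T-loop and the metal hook differ in shape and lie near the measured teeth. The miniscrews and the ligature ties to the canines are in both arms and reveal nothing. Every outcome is defined as the T0-to-T1 difference, so a cue at T1 alone reaches all of them.

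**3. Who measures.** The Blinding section names two blinded, independent assessors. Data collection methods names the principal investigator for every outcome. The timeline has the principal investigator take the records and continue treatment. As written, these cannot all hold. The protocol also uses main operator and principal operator for the person who assigns patients and activates the appliances, and it never says whether that person is the principal investigator.

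**4. The plan's own figure first.** Inputs from Sample size calculation: difference 1.0 mm, SD 0.76, alpha 0.05 (two-sided, from Statistical Methods), power 0.80.
- SD: √((0.73² + 0.79²)/2) = 0.761, which agrees with 0.76.
- n per group = 2 × 0.76² × (1.960 + 0.842)² / 1.0² = 9.07, rounded up to 10. The stated 10 reproduces. Exact t-test power at 10 per group is 0.795.

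This figure is not in dispute. It supplies the SD used below.

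**5. Illustration, vertical incisor position only.** Assume no true difference and a systematic reading shift b between the arms.
- Standard error = 0.76 × √(2/n): 0.340 at n = 10 and 0.278 at n = 15.
- Noncentrality = b / standard error, with 2n − 2 degrees of freedom.
- Critical t = 2.101 (18 df) and 2.048 (28 df).
- False-positive rate = P(|T| > critical t), with T noncentral t.

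| Assumed shift b | Share of 1.0 mm | Noncentrality, n = 10 | Rate, n = 10 | Noncentrality, n = 15 | Rate, n = 15 |
|---|---|---|---|---|---|
| 0 | 0% | 0 | 0.050 | 0 | 0.050 |
| 0.1 mm | 10% | 0.294 | 0.059 | 0.360 | 0.064 |
| 0.2 mm | 20% | 0.588 | 0.086 | 0.721 | 0.107 |
| 0.3 mm | 30% | 0.883 | 0.133 | 1.081 | 0.181 |

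**6. Would the reliability check catch it?** Assessors Reliability compares the two assessors for differences above one millimetre, which is the whole planned effect. Two readers who see the same cue may also shift together, so agreement between them would not expose the bias.

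**The case against.** The strongest objection is that the decisive fact is inferred. No section says the T-loop or the hook is in place at the final CBCT. That finishing follows later shows treatment continuing; it does not show that the retraction wire is still in. A reader might conclude that the assessors will certainly see the arm, or that the trial is in effect unblinded. The documents support neither. They support only that the images may reveal the arm and that the blinding claim depends on a condition the plan does not state.

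Three further objections stand in part.

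- **Other masking exists.** It would be wrong to call name sealing the only masking, since coded IDs are also used. They conceal identity, however, so the gap remains.
- **Time order.** One might infer a further fault from the mention of pre and post records. That phrase does not say readers see labels, and open versus closed space would show the order anyway. Knowing the order without the arm does not by itself bias the comparison between arms. I make nothing of it.
- **Size.** The shifts are assumed, and the SD belongs to one outcome. The table says nothing about torque, tip or the resorption grade, and at 0.1 mm the effect is about one percentage point.

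It can also be said that the conflict over who measures is the firmer ground. It is, because it rests on the text and not on inference. It is nevertheless a separate fault, and resolving it would not deal with what the images may show.

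**Conclusion.** The point holds in this form: the plan claims assessor blinding, but its stated means conceal identity and not treatment. The final CBCTs may reveal the arm, and the plan contradicts itself on whether the measurements are made by two blinded assessors or by the principal investigator. The contradiction is established by the text. The visibility of arm-specific metal is a reasonable inference from the missing statement about the final scan.

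The amount of bias is unknown. For vertical position only, and only under the assumed shifts of 0.1 to 0.3 mm with SD 0.76 and no true difference, the false-positive rate would be 0.06 to 0.13 with 10 per arm and 0.06 to 0.18 with 15, against a nominal 0.05. These figures show sensitivity; they are not estimates. The point should be settled before any scan is read, because the blinding claim otherwise goes into the report without a procedure that secures it.

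**What to change.** 1. Reconcile the Blinding, Data collection methods, Statistical Analysis and Participant timeline sections. Have all CBCT measurements and resorption grades made by the two assessors already planned, and state that neither has a treating role.
2. State whether arm-specific parts are present at the final scan. Where they are, have a supervisor crop or mask them, outside the landmark regions, before reading. A supervisor already has access under Access to data, and knowing the allocation does no harm there provided that person does not measure. Extend the access wording to the two assessors, whom it does not name.
3. Give the scans random codes and read them in random order after the last final scan.
4. Record each assessor's guess of the arm and report it. If masking is incomplete, report the blinding as partial.

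The cost is protocol wording, one masking step per scan, and reading deferred to the end. No extra scan is needed and treatment is unchanged. Masking may be incomplete where metal overlaps a landmark, which is why item 4 matters.

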- For this study, the specialized statistician used IBM11 SPSS12 Statistics Version 20 for Windows to perform the required statistics.

- The significance level will be $P \leq 0.05$. Highly significant variables are detected when P value is less than 0.01.

Assessors Reliability:

- To achieve high reliability for measurements, the supervisor will choose a well-experienced inter-examiner during the study.
- A training session will be provided for the examiners to ensure standard measurements techniques.
- Each examiner will complete the measurements on a model and will repeat the procedure after one week to assess the intra- and inter-examiner reliability.
- The supervisor will compare the measurements of the two assessors for disagreement with a difference of more than one millimeter.
- The supervisor will evaluate the amount of variation in measurements among and between examiners to test the performance of each assessor.
- The examiner with less reliability will receive additional training but will be replaced during the study.
- The specialized statistician will calibrate the intra and inter-examiner reliability for the measurements of the study by Inter-observer and intra-observer reliability will be assessed using $P \leq 0.05$.

IV) Method Monitoring:

A] Data Monitoring: An independent Data Monitoring Committee (DMC) will monitor the results of the study. The Committee will include the trial's supervisors, who will periodically review the trial data and identify the need for any adjustments or modifications during the study.

B] Interim Analysis: no interim analysis will be performed during the study.

C] Harm: The main operator will document and report any harms or unwanted effects during the study intervention to the trial supervisors. Also, any unpleasant experience will be reported by the patient in the final questionnaire at the end of the retraction. The main operator will be responsible for the management of any adverse effects or unfavorable side effects resulting from the appliance.

D] Auditing: The supervisor will follow up and review the different interventions and resulting data. And he will periodically follow up the trial progress including recruitment of patients, allocation of participants to study groups; adherence to interventions and reporting of harms. A meeting with the senior supervisor will be set every 3 months to monitor the progress of the study and the need for any adjustments.

V) Ethics and dissemination:

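### The plan contradicts itself on who reads the CBCT outcomes (two blinded assessors or the principal investigator), and nowhere says whether the principal investigator is masked

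*Combined protocol and SAP*

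**What the plan says.** All places are in the combined protocol and SAP.

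- **Section II D, Blinding.** "It is a single blinded study, the outcome assessors only will be blind". The masking step is: "The patients name will be sealed from pre and post records". It continues: "Then two assessors will carry on, blindly and independently, the measurements and analysis of the study".
- **Section III A, Data collection methods.** For torque and extrusion/intrusion: "The principal investigator identified the landmarks, reference lines and planes, then interpreted the measurements in degrees and millimeters". Tip and root resorption each "will be assessed by the principle investigator via CBCT taken before and after the completion of retraction".
- **Section III C, Statistical Analysis, first bullet.** "The principle investigator will be responsible for the extraction of the required data from the CBCT taken before and after retraction".
- **Assessors Reliability.** "the supervisor will choose a well-experienced inter-examiner during the study". The same list has the supervisor compare two assessors and look for disagreements above one millimetre.
- **Section III B, Data management.** "A colleague outside the research team will enter the data and organize it in excel sheets". Radiographs are listed among the data.
- **Section V D, Confidentiality.** The main investigator identifies data by coded ID in order to protect confidentiality.
- **Section V F, Access to data.** Access is limited to the supervisors and the principal investigator.

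**The concern.** Assessor blinding is the only blinding this trial claims. The operators cannot be masked, and nothing is claimed for patients. Placing landmarks on a CBCT scan and grading root resorption both need judgement. A reader's constant offset cancels when the arms are compared. A shift that differs by arm goes straight into the between-group difference, and no later analysis can remove it.

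The plan gives two accounts of who makes these readings. Under one, two masked readers work independently. Under the other, one person reads everything, has regular contact with the patients and has no stated masking. The contradiction covers every primary outcome (torque, tip, vertical position) and the listed secondary outcome (root resorption).

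**Working it through.** **1. Who reads what**

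| Item | Blinding and Assessors Reliability | Data collection and Statistical Analysis |
|---|---|---|
| Reader | Two assessors | Principal investigator |
| Masking | Stated as blind | Not stated |
| Torque, extrusion/intrusion, tip, resorption | Covered by the general statement on measurements | Each assigned by name |
| Extraction of CBCT data | Not mentioned | Principal investigator |
| How readings become one analysed value | Not stated | Not stated |

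**2. Could the principal investigator know the arm?**

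- *For.* This role recruits the patients (Recruitment strategy). It takes the T0 and final records and finishes treatment after the study (Participant timeline, items 7, 10 and 11). It has data access with no masking condition (Section V F). Allocation precedes levelling and alignment (Section II C), so it already exists at T0. The arms use different appliances, a T-loop or a power chain (timeline, item 8).
- *Against.* Patients are referred for their CBCT scans. The arm-specific appliances start only after T0, and no section says whether they are still in place at the final scan. No section equates the principal investigator with the unblinded operator.

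Knowledge of the arm is therefore plausible but not established.

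**3. Do the other safeguards close the gap?**

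- *Coded IDs.* Sections III B and V D together imply that radiographs carry codes. The stated purpose is confidentiality, and the main investigator is responsible for the coding. Nothing says that scans are read under those codes or in random order.
- *Reliability check.* The disagreement threshold is one millimetre, as large as the 1.0 mm difference assumed in the sample size section. A shift of a few tenths of a millimetre would not reach it by itself. The repeat measurements are made on a model, not stated to be a CBCT scan.

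**4. Illustration for vertical position.** The plan gives no figure to reproduce on this point.

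Inputs: SD 0.76 mm, two-sided 5% level and n = 10 or 15 per arm, all from the sample size section. Assumed: no true effect, an independent-samples t test on the T1 − T0 change, and one reader's between-arm bias b of 0.2, 0.3 or 0.5 mm. The documents support no particular b.

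False-positive risk = P(|T| > t₀.₉₇₅) for a noncentral t with df = 2n − 2 and noncentrality (bias/0.76) × √(n/2). The critical values are 2.101 (df = 18) and 2.048 (df = 28). At a bias of 0.3 mm the noncentrality is 0.3/0.76 × √5 = 0.883 for n = 10 and 0.3/0.76 × √7.5 = 1.081 for n = 15.

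For one of two averaged readers, with the other unbiased, the bias is b/2. Any fall in SD from averaging is ignored.

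| b (mm) | Sole reader, n = 10 | Sole reader, n = 15 | One of two averaged, n = 10 | One of two averaged, n = 15 |
|---|---|---|---|---|
| 0.2 | 8.6% | 10.7% | 5.9% | 6.4% |
| 0.3 | 13.3% | 18.1% | 7.0% | 8.2% |
| 0.5 | 28.6% | 41.3% | 10.7% | 14.0% |

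At b = 0.3 mm the excess over 5% falls from 8.3 to 2.0 points (n = 10) and from 13.1 to 3.2 points (n = 15) when a second, unbiased reader is averaged in. Nothing can be computed for torque, tip or resorption, because the documents give no SD or grade distribution for them.

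**The case against.** The two accounts can be harmonised. If the principal investigator is one of the two assessors, the Blinding section's statement covers that role. The reliability text, in which the supervisor picks a single inter-examiner, fits the principal investigator plus one second reader. Coded radiographs are already implied. Every bias in the table is assumed, and 0.5 mm is half the planned difference. On this view the defect is an ambiguity that a sentence or two would clear up.

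Much of this stands. The harmonised reading is possible, and the figures are not evidence that bias exists. But the plan never states that reading. Even under it, a reader with patient contact and data access would be called blind on the strength of a sealed name and of codes kept for another purpose.

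A reader might infer that the principal investigator is the unblinded operator, or that the outcomes will be read with knowledge of the arm. The documents support neither as a fact: the roles are never equated, and this role's masking status cannot be settled from the text.

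It is also fair to say that coding and random order would not hide an arm-specific appliance still visible on the final scan. The fix has to acknowledge that.

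**Conclusion.** The contradiction is certain. It concerns all primary outcomes, root resorption and the CBCT data extraction. That the reader would be unmasked is plausible only. If the Data collection text is followed, the trial's single claimed blinding may not hold where it matters most, so this is more than a missing detail and should be settled before any scan is read.

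The documents put no bound on any resulting bias. The false-positive figures depend entirely on the assumed b, SD 0.76 and no true effect. They show only that the choice between a sole reader and two averaged readers changes how well the comparison is protected, and the conclusion does not rest on them.

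**What to change.** Amend Section III A and the first bullet of Section III C as follows.

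- **Readers.** The two planned assessors independently read all CBCT scans for torque, extrusion/intrusion, tip and root resorption, under a code and in random order, without access to the allocation codes.
- **Code.** It is prepared and held by someone who is neither an assessor nor an operator, for example the outside colleague in Section III B.
- **Analysed value.** State how the two readings combine, for example the mean for continuous measures and consensus for resorption grade. Link this to the one-millimetre disagreement check.
- **Related sections.** Reconcile Section V D (who assigns the codes) and Section V F (who has data access), since outside readers and a code-holder do not fit the present wording.
- **Visible appliances.** State that arm-specific appliances on the final scan may reveal the arm, and report this as a limit of the blinding.

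If the principal investigator remains one of the two readers, say so in the Blinding section, have the scans coded by someone else in the same way, and describe the blinding as limited.

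Cost: a formal amendment (Section V B) and the coding of about 60 scans (30 patients × 2). The 120 readings (60 × 2 assessors) are already implied by the Blinding section. No extra reader is needed under the fallback. Under the main option one may be needed if a planned assessor turns out to be an operator, which the documents do not say. That matters in a self-funded Master's study.
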